6.7.3. Rescue Lesional Treatments

Rescue lesional treatments are described in Section 8.2.4, as the need for rescue lesional treatment is considered an efficacy assessment.

7. DISCONTINUATION OF STUDY TREATMENT AND PARTICIPANT DISCONTINUATION/WITHDRAWAL

7.1. Discontinuation of Study Treatment

7.1.1. Reasons for Discontinuation

Participants **must** be withdrawn from study treatment for the following reasons:

- The participant becomes pregnant.
- Consent is withdrawn.

Note: Consent withdrawn means that the participant can no longer be followed.

Participants who choose to discontinue study treatment will be encouraged to remain in the study for safety monitoring.

- Further participation would be injurious to the participant's health or well-being, in the investigator's medical judgment.
- The study is terminated by the sponsor.
- The study is terminated by the local health authority, IRB, or IEC.

A participant **may** be discontinued from study treatment as follows:

- If, during the study, a participant is found not to have met eligibility criteria, the medical monitor, in collaboration with the investigator, will determine whether the participant should be discontinued from the study treatment.
- If a participant is noncompliant with study procedures or study drug administration in the investigator's opinion, the sponsor should be consulted for discussion regarding the participant's continued participation.

7.1.2. Discontinuation Procedures

In the event that the decision is made to permanently discontinue the study treatment, the EOT visit should be conducted. Reasonable efforts should be made to have the participant return for an EOT visit. These visits are described in [Table 3](#) and [Section 8.7](#). The last date of the last dose of study drug and the reason for discontinuation of study treatment will be recorded in the eCRF.

If a participant is discontinued from study treatment:

- The study monitor or sponsor must be notified.
- The reason(s) for withdrawal must be documented in the participant's medical record and the primary reason for withdrawal must be included in the eCRF.
- The EOT visit should be performed.

- The date of the EOT visit should be recorded in the eCRF.
- Participants must be followed for safety until the time of the follow-up visit (discontinue date + 30 days) or until study drug-related toxicities resolve, return to baseline, or are deemed irreversible, whichever is longest.

If the participant discontinues study treatment and actively withdraws consent for collection of follow-up data (safety follow-up or disease assessment), then no additional data collection should occur; however, participants will have the option of withdrawing consent for study treatment but continuing in the follow-up period of the study for safety/efficacy assessments.

7.2. Participant Withdrawal From the Study

A participant may withdraw from the study at any time at his/her own request, or may be withdrawn at any time at the discretion of the investigator for safety, behavioral, compliance, or administrative reasons.

If the participant withdraws consent for disclosure of future information, the sponsor may retain and continue to use any data collected before such a withdrawal of consent.

If a participant withdraws from the study, he/she may request destruction of any samples taken and not tested, and the investigator must document this in the site study records.

See [Table 3](#) for data to be collected at the time of study discontinuation and follow-up and for any further evaluations that need to be completed.

7.3. Lost to Follow-Up

A participant will be considered lost to follow-up if he or she repeatedly fails to return for scheduled visits and is unable to be contacted by the study site.

The following actions must be taken if a participant fails to return to the clinic for a required study visit:

- The site must attempt to contact the participant and reschedule the missed visit as soon as possible. The participant will be counseled regarding the importance of maintaining the assigned visit schedule and ascertain whether or not the participant wishes to and/or should continue in the study.
- Before a participant is deemed lost to follow-up, the investigator or designee must make every effort to regain contact with the participant (where possible, 3 telephone calls and, if necessary, a certified letter to the participant's last known mailing address or local equivalent methods). These contact attempts should be documented in the participant's medical record.
- Should the participant continue to be unreachable, he/she will be considered to have withdrawn from the study with a primary reason of lost to follow-up.

8. STUDY ASSESSMENTS AND PROCEDURES

8.1. Administrative and General Procedures

8.1.1. Informed Consent Process

- The investigator or his/her representative will explain the nature of the study to the participant or his/her legally authorized representative and answer all questions regarding the study.
 - Informed consent must be obtained before any study-related procedures are conducted, unless otherwise specified by the Protocol.
 - Informed consent must be obtained using the IRB/IEC-approved version in a language that is native and understandable to the participant. A template will be provided by the sponsor or its designee. The sponsor or its designee must review and acknowledge the site-specific changes to the ICF template. The ICF must include a statement that the sponsor or its designee and regulatory authorities have direct access to participant records.
 - The ICF must contain all required elements and describe the nature, scope, and possible consequences of the study in a form understandable to the study participant.
- Participants must be informed that their participation is voluntary. Participants or their legally authorized representative will be required to sign a statement of informed consent that meets the applicable requirements and regulations for the country in which the study is being conducted as well as the IRB/IEC or study center.
- The participant must be informed that his/her personal study-related data will be used by the sponsor in accordance with local data protection laws. The level of disclosure must also be explained to the participant.
- The participant must be informed that his/her medical records may be examined by Clinical Quality Assurance auditors or other authorized personnel appointed by the sponsor, by appropriate IRB/IEC members, and by inspectors from regulatory authorities.
- The medical record must include a statement that written informed consent was obtained before the participant was enrolled in the study and the date the written consent was obtained. The authorized person obtaining the informed consent must also sign the ICF.
- Participants must provide consent to the most current version of the ICF(s) during their participation in the study.
- A copy of the ICF(s) must be provided to the participant or the participant's legally authorized representative.
- Participants who are rescreened are required to sign a new ICF.

8.1.2. Screening Procedures

Each participant will be identified in the study by a participant ID number, which is a combination of the site ID and participant number.

Screening is the interval between signing the informed consent and the day that the participant is randomly assigned to the study drug (Day 1). Screening assessments for determination of eligibility may be performed over a period lasting up to 28 days.

Procedures conducted as part of the participant's routine clinical management (eg, clinical laboratory tests) and collected before informed consent is obtained may be used for screening or baseline purposes, provided the procedure meets the Protocol-defined criteria and has been performed within 28 days before Day 1. All information associated with eligibility requirements, including demography and medical history, must be entered into the appropriate eCRF pages.

Results from the screening assessments will be reviewed by the investigators to confirm eligibility before randomization and administration of study drug. Tests results that do not meet eligibility requirements may be repeated once during screening if the investigator believes there is a reasonable possibility that the participant would be eligible if retested. For screening assessments that are repeated, the most recent available result before administration of study drug will be used to determine eligibility. See Section [5.4](#) regarding screen failures.

8.1.3. Interactive Web Response System Procedure

Each participant will be identified in the study by a participant ID number, which is a combination of the site ID and participant number. Site personnel should use the IWRS to obtain the participant ID number during screening. Upon determining that the participant is eligible for randomization, the IWRS will be contacted to obtain the treatment assignment. Additionally, the IWRS will be contacted to update the study drug supply (see [Table 3](#)). Additional details are provided in the IWRS manual.

8.1.4. Distribution of Reminder Cards

Participants will be provided with a reminder card at the visits indicated at [Table 3](#). The reminder card will indicate the date/time of the next visit and will also remind the participant that they should not take study drug on Day 1, Week 4, and Week 8 as they will take it after blood draws for safety evaluation have been completed.

8.1.5. Electronic Diary

The date and time of the last dose of study drug and the time of their last meal preceding each PK sample collection visit (see [Table 12](#)) will be recorded in the eCRF. Daily study drug administration HS pain NRS (see Section [8.2.5](#)) and daily analgesic use (see Section [8.2.6](#)) will be recorded in the electronic diary, which will be completed through the web or by phone.

8.1.6. Demography and Medical History

8.1.6.1. Demographics and General Medical History

Demographic data and general medical history will be collected at screening by the investigator or qualified designee and will include date of birth, race, ethnicity, medical and surgical history, and current illnesses. Medical history will include relevant medical or surgical treatment within the last year that are considered to be clinically significant by the investigator.

8.1.6.2. Disease Characteristics and Treatment History

A disease-targeted medical and treatment history will be collected at screening. A detailed history of prior medications use related to HS in the year before screening will be also be collected, as well as response to each treatment and reason for discontinuation.

8.2. Efficacy Assessments

An example of the lesion count worksheet is provided in the Study Manual and will be used for assessment of Hurley Stage, HiSCR, modified Sartorius scale, [REDACTED]. It includes assessment of 12 anatomic regions: left/right axilla, left/right sub/inframammary area, intermammary area, left/right buttock, left/right inguino-crural fold, perianal area, perineal area, and other areas. Additionally, the need for rescue lesional treatment, including number of interventions, will be documented in this worksheet.

8.2.1. Hurley Stages of Hidradenitis Suppurativa

Hurley Stages of HS are defined in [Table 9](#). The investigator will determine the Hurley Stage in each affected anatomical region at the designated study visits listed in [Table 3](#). If more than 1 stage is present in a region, the **worst** stage in each region should be documented. The participant is assigned Hurley Stage corresponding to the Hurley Stage of his or her **worst** involved anatomic region. The Hurley Stages of HS in screening visit is considered as baseline value.

Table 9: Hurley Stages of Hidradenitis Suppurativa

Stage	Description
I	Abscess formation (single or multiple) without sinus tracts and cicatrization.
II	Recurrent abscesses with tract formation and cicatrization; single or multiple, widely separated lesions.
III	Diffuse or near-diffuse involvement or multiple interconnected tracts and abscesses across the entire area.

8.2.2. Hidradenitis Suppurativa Clinical Response (Abscess and Inflammatory Nodule Count)

An HiSCR is defined as at least 50% reduction in AN count with no increase in abscess count and no increase in draining fistula (see definition below) count relative to baseline at each visit (refer to the Study Manual; [Kimball et al 2016](#)).

A fistula is a pathologic passageway connecting to the skin surface from dermis or subcutaneous tissue. Draining fistulas are fistulas that drain serous or purulent fluid, either spontaneously or by gentle palpation.

8.2.3. Modified Sartorius Scale

The modified Sartorius scale is a measure of the severity of HS (refer to the Study Manual; [Sartorius et al 2003](#)).

Points are given as follows for each body area: 2 points for each nodule (both inflammatory and noninflammatory); 4 points for each abscess; 4 points for each fistula (both draining and nondraining); 1 point for each scar; 2 to 6 points for the longest distance between 2 lesions or 0 points if no lesions; and 6 points if lesions are not separated by normal skin or 0 points if lesions are separated by normal skin. The "other area" only with the highest modified Sartorius scale at baseline will be calculated, and the same area should be evaluated throughout the study. The total modified Sartorius scale score is the sum of the 12 anatomic region scores.

8.2.4. Need for Rescue Lesional Treatment

The need for lesional rescue treatment will be recorded as a measure of efficacy.

In the event of an acutely painful lesion that requires immediate intervention, investigators will have the option to perform Protocol-allowed interventions. Two types of interventions are permitted: injection with intralesional triamcinolone acetonide suspension (up to 30 mg in total at the same visit) and/or incision and drainage. If incision and drainage is performed, participants should continue using the same over-the-counter antiseptic as previously. New systemic and topical therapies following incision and drainage, including antibiotics, are prohibited. Concomitant use of wound care dressings is allowed as described in Section [6.7.1.4](#). Participants should continue using any oral and topical therapies during the study, consistent with the allowances and restrictions described in Section [6.7.1](#).

From Day 1 through Week 8 (EOT), an intervention can occur on a maximum of 2 different lesions at the same visit or on the same lesion at 2 different study visits. The same lesion cannot be treated 2 times during the same visit. If participants require more than 2 interventions before Week 8 (EOT), then the study drug will be discontinued for those participants.

Study procedures must be performed before any interventions. Any lesion undergoing an intervention will be documented in the lesion count worksheet (refer to the Study Manual). The site will be required to count any lesion that undergoes an intervention as permanently present from the date of the intervention, and must account for it in the source and on the appropriate eCRF.

8.2.5. Hidradenitis Suppurativa Pain Numeric Rating Scale

The HS Pain NRS (refer to the Study Manual) will be completed in a daily diary by participants from Day 1 through the follow-up visit (EOS). An 11-point scale will be used to assess the worst skin pain and the average skin pain due to HS. Ratings for the 2 items range from 0 ("no skin pain") to 10 ("skin pain as bad as you can imagine"). Assessments will be recorded before bedtime (participants who go to bed after midnight should complete the assessment before midnight) and will be based on a recall period of the last 24 hours.

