4.1.3. Baseline Value

Baseline is the last nonmissing measurement obtained before the first administration of INCB054707 or placebo.

When scheduled assessments and unscheduled assessments occur on the same day and time of the assessment or time of first dose is not available, use the following convention to determine baseline:

- If both a scheduled and an unscheduled visit are available on the day of the first dose and the time is missing, use the scheduled assessment as baseline.
- If all scheduled assessments are missing on the day of the first dose and an unscheduled assessment is available, use the unscheduled assessment as baseline.

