4.1.5. Handling of Missing and Incomplete Data

In general, values for missing data will not be imputed unless methods for handling missing data are specified in relevant sections.

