7.1.5. Hidradenitis Suppurativa Pain Numeric Rating Scale

The HS Pain NRS will be completed in a daily diary by participants from screening through the follow-up visit (EOS). An 11-point scale will be used to assess the worst skin pain and the average skin pain due to HS based on a recall period of the last 24 hours. Ratings for the 2 items range from 0 (no skin pain) to 10 (skin pain as bad as you can imagine).

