7.1.6. Analgesic Use

From Day 1 through the follow-up visit (EOS), participants will complete a daily electronic diary of their analgesic use (yes/no; refer to the Study Manual). All analgesics and dose modifications will be captured in the source and on the appropriate eCRF.

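### The pain diary starts at bedtime on Day 1 in the Protocol but at screening in the SAP; unless a pre-dose Day 1 rating is taken, the SAP rule finds no pain baseline

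*Protocol*

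**What the plan says.** **When the diary starts.** Protocol Section 8.2.5 states that the HS Pain NRS "will be completed in a daily diary by participants from Day 1 through the follow-up visit (EOS". Table 3 agrees: the pain NRS and the diary verification rows are both blank at screening and first marked on Day 1. SAP Section 7.1.5 differs: "The HS Pain NRS will be completed in a daily diary by participants from screening through the follow-up visit (EOS". For the analgesic entries, SAP Section 7.1.6 returns to a Day 1 start: "From Day 1 through the follow-up visit (EOS), participants will complete a daily electronic diary of their analgesic use". Protocol Section 8.1.5 places daily pain and daily analgesic use in one system; both "will be recorded in the electronic diary, which will be completed through the web or by phone". SAP Section 3.4 refers the reader to Protocol Amendment 1 for all assessment schedules.

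**Time of day.** Protocol Section 8.2.5: "Assessments will be recorded before bedtime", and they "will be based on a recall period of the last 24 hours".

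**Baseline.** SAP Section 4.1.3: "Baseline is the last nonmissing measurement obtained before the first administration of INCB054707 or placebo". Protocol Section 10.4.2 is wider. It takes the last nonmissing value up to and including Day 1, unless something else is specified.

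**Missing values.** SAP Section 4.1.5: "values for missing data will not be imputed unless methods for handling missing data are specified in relevant sections". No method is specified for pain.

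**The concern.** Change from baseline in worst and average pain at each visit is a secondary endpoint, listed among the key secondary endpoints in the Protocol summary. It is to be reported in SAP Tables 2.1.3.1 and 2.1.3.2.

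The two documents disagree on when the ratings begin, and the SAP is not consistent with itself on when the shared electronic diary opens. If data are collected as the Protocol's diary section describes and then analysed under the SAP's baseline rule, there may be no eligible baseline value for anyone. The change columns in both tables could not be filled.

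The plan settles this point for some other measures. Protocol Section 8.2.1 names the screening visit as baseline for Hurley Stage, and Table 10 sets a predose Day 1 triplicate as the ECG baseline. Pain has no such statement.

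**Working it through.** No stated figure in the plan bears on this point. The check is a matter of event order, followed by a count of the schedule.

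**Order of events on Day 1**

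1. SAP Section 4.1.1 defines Day 1 as the date of the first dose.
2. Table 3, footnote a, has the Day 1 dose taken at the site. Protocol Section 8.1.4 places it after the safety blood draws, and Table 6 prefers morning dosing.
3. Protocol Section 8.2.5 has pain recorded at bedtime. The Day 1 bedtime rating therefore follows the first dose.

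**Both baseline rules applied to three possible schedules.** Set the first dose at 0 h and assume bedtime on Day 1 at about +12 h. Only the order matters for which value is chosen.

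| Ratings available around Day 1 | SAP 4.1.3 baseline | Protocol 10.4.2 baseline |
|---|---|---|
| Protocol diary only, first entry at Day 1 bedtime (+12 h) | none | +12 h entry |
| Protocol diary plus a rating at the Day 1 visit before dosing (for example −0.5 h) | −0.5 h entry | +12 h entry |
| Diary from screening, as in SAP 7.1.5 (last pre-dose entry at about −12 h) | −12 h entry | +12 h entry |

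In the first row the SAP rule finds nothing. In the other two it finds a value, but not the one that the Protocol's default rule would pick.

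**Size of the gap in the first row**

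- Table 3 pain marks: Day 1, Weeks 1, 2, 4, 6 and 8, and follow-up = 7; screening = 0.
- Visits after Day 1: 7 − 1 = 6.
- Pain items: 2 (worst and average).
- Change-from-baseline summaries per treatment group: 6 × 2 = 12, all empty.
- Participants with an SAP baseline: 0 of about 36.

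In the second and third rows, up to about 36 participants have a baseline.

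**If the Day 1 bedtime entry is used instead.** Its recall window is 24 hours. With the assumed dose-to-bedtime gap of 12 h, 12/24 = 50% of the window is post-dose; each hour more or less moves this by 1/24, about 4 percentage points. If the drug acts within that time, average pain at baseline would be lowered and later improvement understated. Worst pain is a maximum over the 24 hours and may not change. The documents give no onset or effect figure, so the bias cannot be sized.

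**The case against.** The strongest reply is that the empty baseline appears only when parts of two documents are combined. The SAP alone works, because a diary from screening supplies a pre-dose value. The Protocol alone also works, because its own rule accepts a Day 1 value. Table 3 also marks both the pain NRS and diary verification at the Day 1 visit, which would be odd if the first entry were not due until that night. A rating at the visit before dosing would fit the 24-hour recall, and completion by web or phone does not rule it out. Other Day 1 measures, such as the AN count and DLQI, are not labelled predose either. The Study Manual, which Section 8.2.5 cites and which was not available, might settle the timing. The SAP has the same start-date difference for DLQI, which suggests a repeated wording slip.

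Much of this stands. The loss of baseline is conditional, and zero of 36 is the worst case, not a forecast. The stakes are limited: efficacy is exploratory with no p-values, and raw ratings can still be summarised by visit and appear in Listing 2.4.

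The contradiction remains, however. SAP Section 3.4 itself sends the reader to the Protocol's schedule, so combining that schedule with the SAP's baseline rule is what the SAP asks for. The AN count and DLQI are not bedtime diary entries, so the same gap does not arise for them. A manual could clarify what sites do, but it would not make the two documents agree. The Protocol's rule is no clean rescue, since it replaces a missing baseline with a partly post-dose one. SAP Section 4.1.3 can also fairly be read as the specification that Protocol Section 10.4.2 allows for, so the Protocol's rule matters mainly as a fallback.

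**Conclusion.** The point holds. The Protocol and SAP give different start dates for the pain diary, and no text in either says that a Day 1 pain rating is made before dosing. Under the Protocol's bedtime schedule and the SAP's baseline rule, with no separate pre-dose rating, the baseline for worst and average pain is undefined for all of about 36 participants, and 12 change summaries per treatment group are empty. With a pre-dose rating at the Day 1 visit or a diary opened at screening, the SAP baseline exists for up to about 36. Which of these applies cannot be determined from the documents.

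The conclusion rests on two things: the site dose on Day 1 precedes bedtime, and no other text supplies a pain baseline or an imputation. It affects a descriptive secondary endpoint only. The primary safety objective, dose escalation and sample size do not depend on it. It should be fixed, because a pre-dose rating cannot be recovered once dosing has begun.

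**What to change.** **Preferred, while participants can still be rated before dosing.** Align Protocol Section 8.2.5 and Table 3 with SAP Section 7.1.5 so that a pre-dose rating is certain. Either open the web or phone diary during screening, or state that a pain rating is completed at the Day 1 visit before the first dose. In the SAP, name the last nonmissing rating completed before the first dose as the pain baseline. Record the difference from Protocol Section 10.4.2 in SAP Section 10.1, which now reports no changes. That entry is for transparency, since the Protocol's wording leaves room for another rule.

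The cost is a small protocol amendment, which under Protocol Section 11.1 needs IRB/IEC approval before implementation. Opening the diary at screening also adds slight diary burden before Day 1.

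**Fallback, if data were collected from Day 1 only.** Add one sentence to SAP Section 4.1.3 that names the Day 1 entry as the pain baseline, as an exception to the general rule, and discloses that its 24-hour recall is partly post-dose. This needs no new data, but the baseline stays partly post-dose.
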